## 7.2 General Reporting Requirements (Serious & Non-Serious Adverse Events)

All adverse events must be recorded on the Adverse Event CRF by the Investigator (or designee). The report should include: severity, duration, action taken, treatment outcome and relationship of the adverse experience to the study device, procedure, concomitant medications, pre-existing condition, or other factor (i.e., unrelated, related or relationship unknown). The investigative site will report non-serious adverse events into the electronic clinical database within 1 week after they become aware of the non-serious adverse event.

In the case of serious adverse events, procedure and/or device observations and malfunctions, de-identified medical record documentation (e.g. procedure notes, operative notes, discharge summary, relevant progress notes, imaging or lab studies) must be provided to study sponsor or its designee.

*The following criteria must also be adhered to by the Investigator in the case of serious adverse events:*

- The Adverse Event CRF must be signed by the Investigator or Co-Investigator.
- It is the responsibility of the Investigator to inform their IRB of serious adverse events as

The electronic version of this document is stored in Agile PLM and is considered the controlled copy.

Printed copies are for reference only and considered UNCONTROLLED.

CONFIDENTIAL AND PROPRIETARY OF AURIS HEALTH, INC.

 AURIS	PROTOCOL	Doc #:	104-016667-00
	Monarch Uro - Post-Operative Outcomes Study (2023-URO-0001)	Rev:	C
		Page:	29 of 52

required by their IRB procedures and in conformance with FDA and local regulatory requirements.

All serious adverse events must be reported by the Investigator (or designee) to the Sponsor, within 24 hours of learning of the adverse event via CRF. The Sponsor contact information for questions is:

Attn: [REDACTED] PPD MD  
PPD [REDACTED]

### 7.3 Device Failures and Malfunctions

All reported device observations, malfunctions, or failures of the MONARCH™ Platform, Urology will be documented in the CRF. Device failures and malfunctions should also be documented in the patient's medical record.

NOTE: Device failures or malfunctions are NOT to be reported as adverse events. However, if there is an adverse event that results from a device failure or malfunction, that specific adverse event would be recorded in the manner noted in Section 7.2).

Device deficiencies and product complaints reported will be reported via the Auris Complaint Process (email to [contact]) within 1 week of the occurrence. Adverse events and complaints reported to the Sponsor will be reconciled in accordance with the study Safety Management Plan.

## 8. Statistical Methods

The study will enroll up to 60 patients. The Sponsor will be responsible for the analysis of data from this protocol. A detailed Statistical Analysis Plan (SAP) will be written and approved prior to final database lock. The SAP will describe all planned analyses based on the statistical design of this study and the subsequent data collected. A brief overview of key statistical analyses is provided below.

### 8.1 Interval Windows

Interval windows for the purpose of analysis in this study will not be defined outside of those already specified in the protocol for visit scheduling. The final visit occurs approximately 90 days after surgery, thus no interval windows need to be defined given the absence of long-term follow-up in this study. The Schedule of Assessments specifies a window of 7 days around the scheduling of the 30-day follow-up visit, and any information entered in the eCRFs at this visit will correspond to the 30-day visit. The Schedule of Assessments specifies a window of 14 days around the scheduling of the 90-day follow-up visit, and any information entered in the eCRFs at this visit will correspond to the 90-day visit. There will be no assigning of observations to time points outside of the visit to which they are recorded in the eCRFs.

### 8.2 Levels of Significance

No hypotheses are specified for this study and no p-values are being calculated, therefore no level of significance is specified. All estimation of endpoints will be performed using 95% confidence intervals.

The electronic version of this document is stored in Agile PLM and is considered the controlled copy.

Printed copies are for reference only and considered UNCONTROLLED.

CONFIDENTIAL AND PROPRIETARY OF AURIS HEALTH, INC.

	PROTOCOL	Doc #:	104-016667-00
	Monarch Uro - Post-Operative Outcomes Study (2023-URO-0001)	Rev:	C
		Page:	30 of 52

### 8.3 Analysis Sets

The summary of all performance and safety endpoints will be performed on the set of subjects in whom the MONARCH™ Platform, Urology is utilized during the surgical procedure.

### 8.4 Sample Size Justification

No formal hypothesis is being tested in this study; thus, the sample size was not statistically sized, but rather is considered sufficient to inform a baseline assessment on early post-operative outcomes.

### 8.5 Analyses to be Conducted

Categorical variables will be summarized descriptively by frequencies and associated percentages. Continuous variables will be summarized descriptively by number, mean, standard deviation, median, minimum, and maximum. Confidence intervals will also be provided for procedure-related variables. Demographic data will be summarized at the subject level, whereas procedure-related data (including patient-reported outcomes) will be summarized at the procedure level. Any deviations from this general approach will be detailed in the SAP.

Subject disposition will be summarized in total using counts and percentages. The number and percentage of subjects completed and discontinued will be tabulated along with the specific reasons for discontinuation. Subject demographics and surgical characteristics will be summarized.

The number and percentage of procedures achieving successful completion of the robotic-assisted kidney stone removal procedure will be summarized and an exact 95% confidence interval will be estimated.

The number and percentage of procedures resulting in a subject who is determined to be stone free at Day 30 will be summarized and a 95% confidence interval will be estimated. Similar analyses will be performed for the stone-free rate at Day 1. Patient reported outcomes will be analyzed with methodology consistent to the recommendations of the published outcome measure.

All device-related and procedure-related AEs reported during the study will be coded to the Medical Dictionary for Regulatory Activities (MedDRA). All AEs will be summarized by MedDRA system organ class and preferred term by procedure group and in total. Separate summaries will be provided for device-related and procedure-related AEs. Serious AEs will be summarized in a similar manner. Separate summaries by system organ class and preferred term may be provided for events classified as major (Clavien-Dindo Class III or higher) and minor (Clavien-Dindo Class I or II). Separate summaries by Clavien-Dindo grade will be summarized.

Summary statistics will be provided for additional exploratory data points collected in this study. All summaries will be performed only on subjects undergoing the scheduled procedure and only observed data will be summarized. There will be no imputation of data for early terminated subjects or for missing data within the database.

Interim analysis of device safety events will be conducted from the first 20 patients undergoing the study procedure, which is inclusive of this study and a prior clinical study, Initial Experience of the Treatment of Kidney Stones with the MONARCH™ Platform, Urology (104-010990-00). Interim analyses may be conducted to support additional business needs (e.g., abstract submission to scientific conference). Data will also be summarized upon study completion.

The electronic version of this document is stored in Agile PLM and is considered the controlled copy.

Printed copies are for reference only and considered UNCONTROLLED.

CONFIDENTIAL AND PROPRIETARY OF AURIS HEALTH, INC.

 AURIS	PROTOCOL	Doc #:	104-016667-00
	Monarch Uro - Post-Operative Outcomes Study (2023-URO-0001)	Rev:	C
		Page:	31 of 52

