Although kidney stone disease is well associated with pain, with impact to daily activities of life, patient-reported outcomes (PROs) on health-related quality of life in this field are notably not well-established nor commonly studied. The Wisconsin Stone Quality of Life (WISQOL) is a patient survey that was developed to assess the symptomatic and functional impact of stones and has been validated in multiple centers in the United States and Canada. However, there is limited reporting in the use of this survey to differentiate a change in the quality of life following surgical treatment for kidney stones, and a single report using this survey to distinguish between types of surgical intervention. The Patient Reported Outcomes Measurement Information System (PROMIS) are validated questionnaires developed by the National Institutes of Health (NIH) to assess multiple facets of physical, mental, and social health in patients with chronic conditions. The PROMIS-43 subset has previously identified lower quality of life scores in domains of pain and physical function in patients with stone disease. The PROMIS-29 subset recently identified lower scores in the domains of physical function, fatigue, pain interference, depressive symptoms, anxiety, and sleep disturbance in patients with kidney stones, compared to the general US population, with some improvement following ureteroscopy procedures. Early results using PROMIS assessments of pain intensity and interference suggest more sustained improvement in patient-reported scores following PCNL, compared to URS.

Additionally, the impact of residual stone fragments to patient quality of life is even less clear. Only one study has investigated this, and determined that the absence of residual stone fragments, surprisingly, does

The electronic version of this document is stored in Agile PLM and is considered the controlled copy.

Printed copies are for reference only and considered UNCONTROLLED.

CONFIDENTIAL AND PROPRIETARY OF AURIS HEALTH, INC.

	PROTOCOL	Doc #:	104-016667-00
	Monarch Uro - Post-Operative Outcomes Study (2023-URO-0001)	Rev:	C
		Page:	10 of 52

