not necessarily translate to a better quality of life. This study found that patients with residual stones reported similar quality of life outcomes as those who did not have residual fragments. Furthermore, the study also found that among the patients with residual fragments, those who underwent a second surgical procedure reported lower quality of life scores than those who remained under observation. Potentially, this finding is associated with the observation that greater than 73% of these patients who received a secondary procedure did so, despite being otherwise asymptomatic. In this study, alongside the presence of residual fragments, PROs following the mini-PCNL treatment with the MONARCH system will be assessed as an exploratory endpoint, comparing baseline to post-operative Day 1, Day 30 and Day 90 assessments.

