**3.2 Trial Design**

This study is designed as a prospective, single arm study of the robotic-assisted removal of kidney stones using the MONARCH™ Platform, Urology system. Subjects presenting with kidney stones determined to be appropriate for a mini-PCNL procedure per standard medical care and who meet study inclusion and exclusion criteria will be invited to participate. This study will enroll up to 60 subjects. The number of subjects enrolled per site may vary, with maximal enrollments per site determined considering factors such as patient variability, speed of enrollment, and availability of disposable instruments & accessory devices.

The electronic version of this document is stored in Agile PLM and is considered the controlled copy.

Printed copies are for reference only and considered UNCONTROLLED.

CONFIDENTIAL AND PROPRIETARY OF AURIS HEALTH, INC.

	PROTOCOL	Doc #:	104-016667-00
	Monarch Uro - Post-Operative Outcomes Study (2023-URO-0001)	Rev:	C
		Page:	15 of 52

**Inclusion of Left and Right Kidney Procedures within a Subject:** A subject may obtain the study procedure in both kidneys at the discretion of the Sponsor, provided: the case is pre-reviewed with the Sponsor, and the timing of the second study procedure is reasonably not expected to interfere with the interpretation of results from the previous procedure (e.g., causality of any adverse event). Analysis approach for study data is described in Section 8.5. Use of the study device to perform any procedure in a contralateral kidney without prior approval from the Sponsor is not permissible.

**The study device (MONARCH™ Platform, Urology and its Instruments and Accessories) will only be used to perform the study procedure (MONARCH™ mini-PCNL), and none of these components may be used to perform or assist in any other procedure outside of the context of this study (e.g., survey of the contralateral kidney, ureteroscopy in the contralateral kidney).**

[figure not shown]

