## 4.2 Subject exclusion criteria

Pre-Procedure Exclusion Criteria	
Subjects will be excluded from participating in this study if they meet any of the following criteria prior to initiation of the procedure:
 
 
1. Any medical or physical condition/limitation that would contraindicate a conventional ureteroscopy or PCNL in the supine position (e.g., atypical interposition of visceral organs (bowel, spleen, or liver))
 
2. Expected additional procedure, or participation in any clinical trial, from 30 days prior to the study procedure and throughout the duration of the study, which might impact this study's results
 
3. A solitary functioning kidney
 
4. Female subjects who are pregnant or nursing or those of child-bearing potential refusing a pregnancy test
 
5. Presence of ureteral impacted stones
 
6. Presence of ureteral obstruction
 
7. Complete staghorn stone
 
8. Presence of untreated urinary tract infection, urosepsis
 
9. Presence of a renal mass, which has not been investigated
 
10. Tumor in the probable access tract area
 
11. Potential malignant renal tumor
 
12. Subject has an electrically or magnetically activated implanted medical device
 
13. Significant pharmacological anticoagulant therapy or uncorrected bleeding diathesis
 
14. Inability to give consent
 

---	---

In addition, subjects will be excluded from participating in this study if any of the following exclusion criteria occur during the endoscopic procedure.

Intra-Procedure Exclusion Criteria	Any presenting condition discovered intra-procedurally that in the opinion of the investigator would make participating in this study not in the subject's best interest.
---	---

Criteria identified intraoperatively to justify patient exclusion, will be reviewed by the Sponsor, and considered for articulation directly in the protocol for future cases to ensure consistency in exclusion.

	PROTOCOL	Doc #:	104-016667-00
	Monarch Uro - Post-Operative Outcomes Study (2023-URO-0001)	Rev:	C
		Page:	24 of 52

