## 8.7 Additional Endpoints

Summary statistics will be provided for the following:

- Procedure duration: defined as the difference between “When was the patient’s percutaneous wound closed?” from the Mini-PCNL eCRF and “When is the Cystoscope introduced?” from the Pre-Procedure Setup eCRF
- Cumulative stone burden at the 30-day follow-up visit as well as change in stone burden from the Screening/Baseline visit; Change in cumulative stone burden (%) will also be summarized and is defined as  $100 \times (\text{Change}/\text{Baseline})$ . Similar analyses will be presented for cumulative stone volume at the 30-day follow-up visit.
- Efficiency of stone ablation defined as pre-operative stone volume divided by lithotripsy time. Lithotripsy time is defined as the difference between the treatment complete time from the mini-PCNL eCRF and first lithotripsy start time on the Laser Settings eCRF.
- Placement of a stent or nephrostomy tube as well as duration of stent placement in days: defined as the difference between “Date of stent extraction” from the Physical Exam and Vital Signs eCRF at the 30-day visit and “Did you place a ureteral stent in this patient?” from the Mini-PCNL eCRF + 1
- Subject weight post-procedure as well as change from pre-procedure weight
- Length of stay in nights: defined as “Date of hospital discharge” – “Date of hospital admission”
- Selected labs taken immediately post procedure (sodium, creatinine, hematocrit) as well as change from the Screening/Baseline visit
- Total fluoroscopy dosage (mGy) and time (minutes)
- Percutaneous access fluoroscopy dosage (mGy) and time (minutes)

- Wisconsin Stone Quality of Life survey over time as well as change from baseline (overall score and individual domains of social impact, emotional impact, disease impact and vitality impact)
- PROMIS-29 Profile v2.1 survey over time as well as change from baseline (overall score and individual domains of physical function, anxiety, depression, fatigue, sleep disturbance, social role satisfaction, and pain interference).

Counts and percentages will be provided for the following:

- Number and location of post-operative stones at the Day 1 and Day 30 follow-up visits.
- Number of needle attempts
- Need to relocate stones
- Number of Randall's plaques in each of the Upper Pole, Interpole, and Lower Pole as reported in the Investigator Assessment eCRF

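### Whole-person quality-of-life scores are summarised per procedure, so any patient treated in both kidneys counts twice, and a staged second procedure normally starts from a score taken after the first operation

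*Protocol*

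**What the plan says.** **Unit of analysis.** Protocol 8.5 puts demographics at the subject level, but "procedure-related data (including patient-reported outcomes) will be summarized at the procedure level". It leaves any departure from this to the SAP.

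**Two kidneys.** Protocol 3.2: "A subject may obtain the study procedure in both kidneys at the discretion of the Sponsor". The conditions are that the sponsor reviews the case beforehand and that "the timing of the second study procedure is reasonably not expected to interfere with the interpretation of results from the previous procedure". The one example given is adverse-event causality, and no minimum interval is stated. For the analysis, 3.2 refers to 8.5, which has no rule for a second procedure's patient-reported outcomes (PROs).

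**Eligibility.** Protocol 4.2, exclusion 2, covers "Expected additional procedure, or participation in any clinical trial, from 30 days prior to the study procedure and throughout the duration of the study", limited to those that might affect the results. It does not say how it relates to the bilateral allowance.

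**Instruments and timing.** Protocol 2.1 says PROMIS was developed "to assess multiple facets of physical, mental, and social health in patients with chronic conditions", and makes PROs an exploratory endpoint that compares baseline with Days 1, 30 and 90. Table 1 allows ±7 days at Day 30 and ±14 days at Day 90.

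**SAP.** Section 8.7 plans the "Wisconsin Stone Quality of Life survey over time as well as change from baseline", and treats PROMIS-29 the same way. It names no unit and no departure from the protocol. Section 8.1 takes as baseline, for every parameter, the latest measurement no later than the procedure date. Section 8.12 plans no sensitivity analysis. Bilateral subjects are not mentioned anywhere.

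**The concern.** A stone, a tract or a laser time belongs to one kidney, so the procedure is a natural unit for it. Anxiety, fatigue, sleep and social role belong to the patient. When a patient has two study procedures, a procedure-level summary takes that person's scores twice. The SAP baseline rule then picks, for the second procedure, whatever score came last before it, which is normally one from recovery after the first. A second operation inside the first procedure's follow-up can also affect the scores attributed to the first.

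At stake is the mean change in quality of life after MONARCH mini-PCNL. This is one of the additional objectives in Protocol 2.2. The tables would mix change from an untreated state with change from a state in which the other side has already been operated on. The displayed n would also exceed the number of people.

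**Working it through.** The documents give no PRO mean, standard deviation or bilateral count, so there is no figure of theirs to reproduce. Two checks apply.

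**1. Timing.** Let t be the days from first to second procedure. Compare t with the PRO visits at Days 1, 30 and 90 (the last at most 90 + 14 = Day 104) and with the SAP 8.1 baseline rule. Visits are taken at their nominal days unless stated.

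| t (days) | First procedure's PROs that can follow the second operation | Second procedure's baseline under SAP 8.1 |
|---|---|---|
| 0 (same day) | all, for both procedures alike | pre-operative score, used twice |
| 1–29 | Day 30 and Day 90 | first procedure's Day 1 score |
| 30 | Day 30 (if taken after it) and Day 90 | first procedure's Day 30 score, if already taken |
| 31–89 | Day 90 | first procedure's Day 30 score |
| 90 | Day 90 (if taken after it) | first procedure's Day 90 score, if already taken |
| 91–104 | only a late Day 90 visit | first procedure's Day 90 score, if already taken |
| over 104 | none | first procedure's Day 90 score |

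A fresh PRO taken between the operations would replace the baseline shown, but it too follows the first operation. Only if no score was taken in between would the rule fall back on the original pre-operative one. So double counting arises at every t, the post-operative baseline is the normal result at every t above 0, and carry-over into the first procedure's follow-up needs t of at most 104.

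**2. Illustration of size, under assumptions.** Take n = 60 subjects (the planned maximum; SAP 1.2 says enrolment stopped below it), b of them bilateral, and m = n + b procedures. The bilateral shares of 0%, 5%, 10% and 20% are assumed. All results depend only on b/n, so smaller enrolment with the same share gives the same values.

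- Share of records from bilateral patients = 2b/m.
- Mean change relative to the first-procedure change = (n + b·g)/m. Here g is the second procedure's gain from its own baseline as a fraction of the first's. This assumes that first-procedure gains are equal in all subjects and free of carry-over.
- True SE divided by the SE that treats records as independent = √((m + 2bρ)/m), where ρ is the correlation between a patient's two records, assumed 0.3 to 1.0. Coverage of a nominal 95% interval = 2Φ(1.96/ratio) − 1.

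| b | m | 2b/m | Mean factor, g = 0 | Mean factor, g = 0.5 | SE ratio, ρ = 0.3 to 1.0 | Coverage |
|---|---|---|---|---|---|---|
| 0 | 60 | 0% | 1.00 | 1.00 | 1.00 | 95% |
| 3 | 63 | 9.5% | 0.952 | 0.976 | 1.014–1.047 | 94.7–93.9% |
| 6 | 66 | 18.2% | 0.909 | 0.955 | 1.027–1.087 | 94.4–92.9% |
| 12 | 72 | 33.3% | 0.833 | 0.917 | 1.049–1.155 | 93.8–91.0% |

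For example, with b = 12 and g = 0 the mean factor is 60/72 = 0.833, and with ρ = 1 the SE ratio is √(96/72) = 1.155. If second procedures gain as much as first ones (g = 1), the mean factor is 1.00 throughout. The column 2b/m counts exposed records; it does not measure bias. The coverage column matters only if an interval is reported. Protocol 8.5 promises intervals for procedure-related variables, but SAP 8.7 lists only summary statistics for PROs.

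With one record per subject, m = n and both factors are 1.00 by construction.

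**The case against.** The strongest reply is that the plan already guards against interference. Sponsor pre-review and the timing condition in Protocol 3.2 are aimed at it, adverse-event causality is only an example, and Day 30 and Day 90 PROs are results too. A second operation inside the first's follow-up may be just what the sponsor would refuse. This stands in part. The condition reduces carry-over into the first procedure's follow-up, although it names no interval. It protects only the previous procedure's results, so it does nothing for the second baseline or for double counting. Exclusion 2 does not settle the matter either, because 3.2 expressly permits the second procedure.

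A second reply is that change from the last score before each operation is a coherent per-procedure quantity, chosen deliberately. It is coherent, but averaging it with change from an untreated state gives a mean that describes neither, and the person is still counted twice.

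A third reply is that the SAP reads as if no bilateral patient exists. It was written after enrolment stopped, tabulates the treated side per subject (8.4), counts subjects for the primary endpoint (8.5), and speaks of a single procedure date (8.1). It also lists all data per subject, which keeps repeat patients visible. All this is consistent with few or no bilateral patients but does not establish it.

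A reader might also infer from Protocol 2.1 that second operations lower these scores, since it reports that "those who underwent a second surgical procedure reported lower quality of life scores than those who remained under observation". That finding concerns retreatment of patients with residual fragments, not study surgery on the opposite kidney, and is not evidence for this point.

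**Conclusion.** The point holds as a conditional flaw in a stated rule. If any subject is bilateral, the plan as written counts that person twice in every PRO summary. If that subject's procedures are staged, the second one's baseline will normally be a score taken after the first operation. If the second operation comes no later than Day 104 of the first and before its last PRO visit, the first's follow-up scores can be affected as well.

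A reader might infer more: that second operations do contaminate first follow-ups, or that the PRO results are biased. The documents do not support either. Contamination depends on timing that the sponsor is required to review, the baseline problem does not arise with same-day treatment, and the number of bilateral subjects is not given and may be zero.

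The endpoint is exploratory and descriptive, with no hypothesis or p-value. The illustrated mean factors of 0.95 to 0.83 rest on an assumed 5% to 20% bilateral share and no further gain at second procedures. They show what could happen, not an estimate. The change is worth making because it is cheap, and the primary and secondary endpoints are untouched.

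**What to change.** State the departure in SAP 8.7. Protocol 8.5 already leaves departures to the SAP, so the protocol needs no amendment. Suggested text:

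> PROs are summarised at the subject level. The index is the subject's first study procedure, and baseline is the pre-operative score before it. PRO scores taken after a later second study procedure are listed and are not included in the change-from-baseline tables. Treatment of both kidneys on the same day counts once. The number of bilateral subjects and the intervals between their procedures are reported.

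The cost is SAP wording and a date filter on data already collected. If the SAP is already approved, its section 8.1 calls for a SAP amendment. The downside is that a few late PRO scores from bilateral subjects move from the summary tables to listings. If there are no bilateral subjects, no result changes. The fix concerns analysis only and sets no rule on when a second kidney may be treated.
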